Statistical Methods, Data Analysis and Interpretation

Data analysis: We will use 3 factors with two options each and a narrative information sheet for the factorial experiment. We will have 16 different study conditions. Standard psychometric analyses (e.g., Cronbach's alpha) will be used to confirm the internal consistency reliability of self-report measures. For our primary outcome variable PrepDM, we will use a 4-way ANOVA model to describe differences in decision preparedness across each factor (e.g. ambiguity, complexity, normalizing and explanatory language, and narrative information sheet) (4). We will use post-fit marginal estimation to express effect sizes (adjusted means and adjusted mean differences), which incorporates mean centering to make the main effects interpretable in the presence of factor interactions. Regression models, with main effect and interaction terms, can be fitted that are identical to a 4-way ANOVA model. We will use these to model the secondary outcomes, using binary logistic, ordinal logistic, and linear regression, depending on the level of measurement of the outcome variable, and will add race and education level as covariates in all models. We will perform exploratory analyses for populations with and without NMS and by ethnicity and language.

Sample size: In a validation study of PrepDM in orthopedic decision making, the scale had mean SD of 3.7+/-1.0 after the decision aid intervention (4). We will randomize n=46 subjects into each of the 2x2x2x2=16 cells of the 3-way factorial design (each factor at 2 levels), for a total N=736 subjects. This is a sufficient sample size to include 4 main effects, 3 two-way interactions, 2 3-way interaction, and 1 4-way interaction, without overfitting the data. This provides 95% power, using a two-sided alpha 0.05 comparison, to detect an adjusted mean difference of 3.7+/-1.0 vs. 3.4+/-1.0 (0.3 standardized mean difference) between the two levels of the factor. That is smaller than a 0.5-point difference on the scale of each item and has been achieved in previous studies of decision aids in orthopedics.

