STATISTICAL ANALYSIS PLAN

Understanding Factors in Decision Making for Children With Medical Complexity

NCT number: NCT05913206

Last reviewed: August 29, 2025

PI: [name], MS

General Considerations

This randomized factorial experiment examines the effectiveness of uncertainty communication statements and parent narratives for parents of children with medical complexity (CMC). The experiment was nested within a video vignette of a family's visit to a pediatric orthopaedic surgeon regarding potential surgery treatment of their child's neuromuscular scoliosis (NMS). The trial includes 16 possible scenarios based on 4 factors (ambiguity, complexity, normalizing and explanatory language, and narratives) with 2 levels each (present, absent). Participants underwent stratified randomization by language, site, ethnicity, and race.

Study Objectives and Hypotheses

The main objective of the study is to evaluate the effect of various uncertainty communication statements and narratives on decision readiness and additional cognitive, behavioral, and affective outcomes related to decision quality and risk perception.

We hypothesize that participants who receive uncertainty statements and/or narratives will report higher decision readiness without experiencing detrimental effects of increased worry or decreased hope. We hypothesized that these effects would be summative across factors.

Study Design

All participants were recruited from two sites. Eligible parents were at least 18 years old and had a child 0-21 years of age with medical complexity. Randomization was conducted using REDCap, a HIPAA compliant remote data capture system. Participants were not explicitly informed of their group assignment.

The specific trial arms are:

Control condition: Participants in the control condition received a vignette reflective of a typical orthopaedic surgery clinic visit to discuss neuromuscular scoliosis treatment without the addition of any uncertainty communication statements or exposure to parent narratives.

Ambiguity only: This intervention group received a vignette with ambiguity statements embedded in the video.

Complexity only: This intervention group received a vignette with complexity statements embedded in the video.

Normalizing and explanatory language only: This intervention group received a vignette with normalizing and explanatory language about uncertainty embedded in the video.

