Participants who complete the study will be analyzed in the group to which they were randomized, regardless of fidelity. A two-tailed alpha level of 0.05 will be applied to all statistical tests. For the outcomes, we will use standard psychometric analyses (e.g., Cronbach's alpha) will be used to confirm the internal consistency reliability of self-report measures. For the primary outcome variable PrepDM, we will use a 4-way ANOVA model to describe differences in decision preparedness across each factor (ambiguity, complexity, normalizing and explanatory language, and narratives). We will use post-fit marginal estimation to express effect sizes (adjusted means and adjusted mean differences), which incorporates mean centering to make the main effects interpretable in the presence of factor interactions. Regression models, with main effect and interaction terms, can be fitted that are identical to a 4-way ANOVA model. We will use these to model the secondary outcomes, using binary logistic, ordinal logistic, logistic regression for proportions, and linear regression, depending on the level of measurement of the outcome variable, and add covariates including race and education level to all models. We will select covariates using the 10% rule. If we have sufficient power, we will perform exploratory analyses for populations with and without NMS and by ethnicity and language.

Although multiple outcomes will be considered, we have designated a single primary outcome. We do not plan formal multiple comparison adjustments for secondary and exploratory outcomes. Results for secondary and exploratory outcomes will be interpreted based on the overall pattern of results with the awareness that some nominally significant relationships may be false positive findings in the context of multiple analyses.¹⁰

We also do not plan formal multiple comparison adjustments for the randomized comparison between intervention groups, as these comparisons address distinct hypotheses and are thus appropriate for evaluation on a comparison wise basis.¹⁰

Missing data

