We will use careful data collection and data management to minimize missing data. If missing data are present in Aim 1 or Aim 3, we will explore patterns of missingness and then impute missing data. We will use the multivariate imputation via chained equations (MICE) approach on both the outcome and predictor variables to create 40 imputed data sets (Graham, et al. 2007)¹⁴⁸, after which coefficients and standard errors are combined using Rubin's rules (Rubin, 1987).¹⁴⁹

Sample size and power calculation for the primary analysis

In a validation study of PrepDM in orthopedic decision making, the scale had mean \pm SD of 3.7 \pm 1.0 after the decision aid intervention. We will randomize n=91 subjects into each of the 2x2x2x2=16 cells of the 4-way factorial design (each factor at 2 levels), for a total N=728 subjects. This is a sufficient sample size to include 4 main effects, 4 two-way interactions, and 3 3-way interactions, without overfitting the data. This provides 80% power, using a two-sided alpha 0.05 comparison, to detect an adjusted mean difference of 3.7 \pm 1.0 vs. 3.4 \pm 1.0 (0.3 standardized mean difference) between the two levels of the factor. That is smaller than a 0.5-point difference on the scale of each item and has been achieved in previous studies of decision aids in orthopedics.

References

2. O'Connor AM. Validation of a Decisional Conflict Scale. *Medical Decision Making*. 1995/02/01 1995;15(1):25-30. doi:10.1177/0272989X9501500105
4. Institute NC. Health Information National Trends Survey (HINTS). Accessed August 5, 2020, 2020. <https://hints.cancer.gov/default.aspx>

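### The stated powers of 80% (SAP) and 95% (protocol) do not follow from their own inputs, which give about 98%. Both interaction lists fail to match the planned 4-way ANOVA, and no precision is given for judging the summative hypothesis.

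*SAP*

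**What the plan says.** The SAP, under Sample size and power calculation for the primary analysis, puts 91 participants in each of 16 cells and gives a total of 728. It then states: "This provides 80% power, using a two-sided alpha 0.05 comparison, to detect an adjusted mean difference of 3.7" versus 3.4, each with SD 1.0. It describes the contrast as "0.3 standardized mean difference) between the two levels of the factor".

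The Sample size paragraph of the protocol (Statistical Methods, Data Analysis and Interpretation) puts 46 in each of 16 cells, total 736, and states: "This provides 95% power, using a two-sided alpha 0.05 comparison, to detect an adjusted mean difference of 3.7+/-1.0 vs. 3.4+/-1.0". The SD comes from a validation study in which "the scale had mean SD of 3.7+/-1.0 after the decision aid intervention". The protocol's Inclusion Criteria give 1,008 for the factorial experiment.

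On model terms, the SAP says: "This is a sufficient sample size to include 4 main effects, 4 two-way interactions, and 3 3-way interactions, without overfitting the data". The protocol says: "This is a sufficient sample size to include 4 main effects, 3 two-way interactions, 2 3-way interaction, and 1 4-way interaction, without overfitting the data". Both documents name a 4-way ANOVA as the primary analysis and say that regression models identical to it can be fitted.

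On significance, the SAP says: "A two-tailed alpha level of 0.05 will be applied to all statistical tests". It plans no multiplicity adjustment for the comparisons between intervention groups.

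Under Study Objectives and Hypotheses, the SAP adds: "We hypothesized that these effects would be summative across factors". No test, margin, precision or power is attached to that hypothesis in either document.

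**The concern.** The two documents give the same effect, SD and alpha, and totals that differ by 8, yet their powers differ by 15 percentage points. At least one must be wrong, and the size of the contrast suggests that both are.

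The term lists disagree with each other and with the named model. If a list is taken as the model specification, the analyst has to decide which interactions to leave out, and nothing in the plan says which.

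Additivity across factors is a statement that interactions are absent or small. The plan makes additivity a hypothesis but does not say how precisely the interactions will be estimated. A reader therefore cannot tell what the data could show about it.

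**Working it through.** **Inputs.** Difference 0.3, SD 1.0 and two-sided alpha 0.05 (both documents). Totals: 728 (SAP), 736 = 46 × 16 (protocol Sample size), 1,008 = 63 × 16 (protocol Inclusion Criteria), and 1,456 = 91 × 16 (the SAP's own cell size; 728 is 91 × 8). Equal cells and no missing data are assumed; neither sample-size section gives a dropout rate.

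**Step 1: reproduce the stated powers.** With N/2 per level, SE(main effect) = 2 × SD/√N and power ≈ Φ(0.3/SE − 1.96).

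- SAP, N=728 (364 v 364): SE = 2/√728 = 0.0741; 0.3/0.0741 = 4.05; power = Φ(2.09) = 98.2% (98.1% by noncentral t on N − 16 df). Stated: 80%.
- Protocol, N=736 (368 v 368): SE = 2/√736 = 0.0737; 0.3/0.0737 = 4.07; power = Φ(2.11) = 98.2%. Stated: 95%.

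Neither reproduces. In reverse, n per level = 2 × (1.96 + z)²/0.3². This gives 175 per level (350 in total) for 80% and 289 per level (578 in total) for 95%.

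**Step 2: look for a reading that does reproduce them.** A simple effect of one factor within one level of another (182 v 182 at N=728) gives 81.6%, near the SAP's 80%. At N=736, a Bonferroni correction for three factors gives 95.3% and 20% dropout gives 95.4%, near the protocol's 95%. The documents state none of these readings, and the SAP plans no adjustment for these comparisons.

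**Step 3: count the terms.** Four factors give C(4,1) = 4 main effects, C(4,2) = 6 two-way, C(4,3) = 4 three-way and C(4,4) = 1 four-way interaction.

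| | two-way | three-way | four-way |
|---|---|---|---|
| Full 4-way ANOVA | 6 | 4 | 1 |
| SAP list | 4 | 3 | 0 |
| Protocol list | 3 | 2 | 1 |

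The full model has 16 parameters with the intercept, leaving 728 − 16 = 712 residual degrees of freedom at the smallest of the four totals. Overfitting is no reason to shorten the list.

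**Step 4: interactions, as an illustration.** Define a two-way interaction as a difference of differences, so SE = 4 × SD/√N. The documents give no interaction effect; 0.3 SD is an assumption, borrowed from the main effect. The 80% detectable difference is (1.96 + 0.84) × SE.

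| Total N | Main effect 0.3 SD: power | Detectable main effect (80%) | Two-way 0.3 SD: power | Detectable two-way (80%) |
|---|---|---|---|---|
| 728 | 98.2% | 0.21 SD | 52.5% | 0.42 SD |
| 736 | 98.2% | 0.21 SD | 53.0% | 0.41 SD |
| 1,008 | 99.7% | 0.18 SD | 66.3% | 0.35 SD |
| 1,456 | >99.9% | 0.15 SD | 81.6% | 0.29 SD |

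The interaction power depends heavily on the assumed effect. At N=728 it is 17% for 0.15 SD, 52.5% for 0.3 SD and 98.2% for 0.6 SD. The standard error at N=728 is 4/√728 = 0.148 SD, so a 95% confidence interval extends about 1.96 × 0.148 = 0.29 SD either side of the estimate.

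The protocol's Randomization paragraph also still describes eight versions with 63 parents each (504). At that total, main-effect power is 92.0%, which again matches neither stated figure.

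**The case against.** The strongest reply is that the error does no harm to the primary comparisons. The power statements concern the two levels of one factor, and at all four sixteen-cell totals both documents understate the power. No test, estimate or alpha changes. The SAP describes randomization in the past tense, so the correction is to documentation. All of this stands. It limits the seriousness of the point but does not make the figures right.

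Several stronger readings are tempting, and the documents do not support them.

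- *The true interaction power is 52% and the plan misstates it.* The plan states no interaction effect or power, so there is no figure to correct. The 52% rests on an assumed 0.3 SD difference of differences at N=728. If the interaction effect is instead defined as half the difference of differences, as is common in two-level factorials, 0.3 SD has the same 98% power as a main effect.
- *The plan promises equal assurance for interactions.* Both power statements are confined to a factor's two levels.
- *A non-significant interaction will be read as proof of summativity.* Neither document says so. The SAP plans adjusted means and mean differences, which is estimation. The gap is that it does not say how summativity will be judged.
- *The term lists make the analysis impossible.* The sentences say what the sample can support without overfitting, and a model with some interactions omitted can be fitted. In roughly balanced cells, omission would barely move the main-effect estimates. The lists still contradict each other and do not describe the named model.
- *The 80% was computed for 182 v 182.* The match is close, but this is a guess about its origin.

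**Conclusion.** The stated powers and term lists are wrong as written. For a 0.3 SD main effect, power is about 98% at both 728 and 736, not 80% or 95%. Neither stated figure is right at any other total in the documents. The interaction counts should be 6, 4 and 1 for the planned ANOVA. These conclusions rest on SD 1.0, equal cells and no missing data; with 20% dropout, main-effect power would still be about 95% at N=728 or 736.

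The missing precision for interactions is an omission, separate from the miscalculated power, and its size depends on an unresolved N and an unstated effect. A reader might infer that the trial is too small for its primary contrasts. The reverse holds at each of the four sixteen-cell totals. The point calls for a correction to both documents, but it does not threaten the validity of the main-effect analysis.

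**What to change.** 1. Reconcile cell size and total N across both documents before restating any power. The candidates are 728, 736, 1,008 and 1,456, and the protocol's eight-version Randomization text should be brought into line at the same time.
2. For the reconciled N, state the main-effect power for 0.3 SD and the 80% detectable differences, for both a main effect and a two-way difference of differences, using the matching row of the table above. Say which definition of interaction is used, and state any allowance for dropout.
3. Correct the term list to 4 main effects, 6 two-way, 4 three-way and 1 four-way interaction. If terms are omitted deliberately, name them and give the reason.
4. State in the SAP that summativity will be judged from the six two-way interaction estimates with 95% confidence intervals, and not from non-significance.

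The cost is wording in the SAP and protocol. Apart from settling which N applies, neither recruitment nor conduct has to change. The main-effect figure becomes more favourable, and the limited precision for interactions becomes visible.
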